10.1 Screening/Enrolment procedure (Consent Form)

All potential participants in this study must provide informed consent before any study related procedures are undertaken. The nature of the study will be explained by the investigator and any questions that the participant has should be addressed. If in agreement to proceed with the study, participants will then need to sign the Participant Informed Consent Form. Participants will be provided with a copy of the Participant Informed Sheet.

At the screening visit, Professors [name] or [name], or other neurologists involved in the study will:

- Provide detailed study information
- Review eligibility check list

- Obtain signed informed consent (if participant already willing)
- Complete procedures that are part of patient best standard of care, namely:
- (i) Review history of first demyelinating event (KFS, EDSS, and Multiple Sclerosis Functional Composite (MSFC)
- (ii) Review medical history,
- (iii) Review medication history,
- (iv) Arrange a gadolinium-enhanced cerebral MRI (standard of care)(digital copy of films to be retained for PhoCIS), and
- (v) Prescribe vitamin D supplementation to obtain a serum 25(OH) vitamin D level of approx. 100 nmol/L

If the participant wishes to discuss participation in the study with their family or friends, they may request that one of the project co-ordinators contact them within a week to further discuss participation in the trial. Verbal consent can be given over the telephone. A 'Baseline' visit with a member of the study team will be arranged and written consent obtained. This visit will confirm that eligibility to participate in this study and any questions that you may have will be answered. This visit will take about 1.5 - 2 hours.

The following will be performed at the Baseline visit (if not already done):

- (1) Blood collected for baseline measurement of biological molecules (biomarkers) and collection of blood cells for studies of their biological activity,
- (2) Questionnaires completed about your symptoms and its effect on your health and quality of life, including the Quality of Life Questionnaire (SF36v2), Fatigue Severity Scale, Lifestyle Questionnaire (see Appendix),
- (3) A serum and urine pregnancy test (female subjects only),
- (4) Anthropometric measurements (weight, height, waist and hip circumference), blood pressure. Participants will be asked to remove clothing to allow waist and hip measurement and placement of a blood pressure cuff on their arm
- (5) Eye/skin/hair colour assessment
- (6) Assessment of skin reflectance and preparation of a silicone cast of the back of the hand as a measure of past sun exposure
- (7) Saliva collection for EBV analysis.

10.2 Post-screening

Upon successful completion of the screening process (pregnancy test that was negative and all inclusion and exclusion criteria confirmed), eligible participants will be enrolled into the study. Eligible participants will then be randomised into one of two treatment groups, namely to receive phototherapy or not to receive phototherapy.

10.3 Treatment schedule

Narrow band UVB phototherapy will be given three times/week for eight weeks (24 exposures in total). Narrow band UVB phototherapy will be delivered according to the Dundee protocol which is based on the participant's skin type. The starting dose of 20 mJ/cm² is chosen based on knowledge of the skin type and will be well below the likely erythema threshold. All participants will start with 40% increments on their initial dose, which will be reduced to 20% increments after 6 exposures. At each visit the dose given and any adverse effects will be recorded by [name], or her experienced study nurses.

[name] will assess the skin of the participants before and 6 months after initiation of phototherapy, and during the trial if the participants have any concerns.

Narrow band UVB phototherapy will be initiated as soon as possible for those who are not prescribed a short course (few days) of glucocorticoids for treatment of their first demyelinating event.

If participants randomised to receive narrow band UVB phototherapy have been given a short course of glucocorticoids to treat their symptoms, the participants will be asked to commence UVB phototherapy in one month after completion of glucocorticoids. This will allow a drug-washout period and normalization of their immunological biomarkers. After this 'washout period' and immediately prior to the start of phototherapy, they will be asked to donate 50 ml blood for pretherapy measurement of biomarkers and collection of peripheral blood mononuclear cells for functional assays.

All participants will be required to wear a UVB dosimeter for 8 weeks. The UVB dosimeters will be used to collect daily UVB exposure data for these participants.

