been reported [2]. The face and eyes are protected during sessions of otherwise total body irradiation. Multiple mechanisms are involved in the control of psoriasis by narrow band UVB, including reduced inflammatory DCs infiltrating the skin [41], increased regulatory T cell number and function [8] and modulation of the IL-17/IL-23 axis [41].

A search of the literature has not revealed any studies of phototherapy for MS patients. There was one study of extracorporeal photochemotherapy used in 5 patients with refractory Relapsing Remitting MS with some success [42]. Phototherapy for MS patients is also supported by demonstration that UVR can suppress the severity of experimental autoimmune encephalomyelitis (a murine model of MS) when there were minimal changes in serum 25(OH)D levels [43].

This trial of narrow band UVB phototherapy will be documented in compliance with the protocol, GCP and the applicable regulatory requirements.

Description of the population to be studied. Patients at high risk of MS [patients with CIS defined by a First Demyelinating Event (FDE)].

7. Hypothesis, Aims and Objectives

Hypothesis: Narrow band UVB phototherapy will benefit patients with CIS; it will alter in a sustainable manner the immunological biomarkers in blood that are associated with subsequent transition to clinically-definite MS. UVB phototherapy will increase the ratio of regulatory to effector T lymphocytes, reduce the functional capacity of circulating dendritic cells (DCs), and ensure that the transcriptional profile in their peripheral blood mononuclear cells is similar to one associated with healthy controls and not one characterised for MS patients.

Aims and Objectives of the PhoCIS trial: In 30 patients with CIS given a course of narrow band UVB phototherapy (3 exposures/week for 8 weeks) and 30 CIS patients without phototherapy wearing UVB dosimeters, we will examine whether:

- 1. UVB phototherapy reduces the risk of a recurrent disease activity (clinical demyelinating event or MRI activity) in the 12 months following onset of a first demyelinating event.
- 2. UVB phototherapy affects the clinical and/or radiological responses associated with development of MS in high-risk CIS participants.
- 3. UVB phototherapy alters the phenotype, function and transcriptional profile of immune cells in blood drawn 1 week, and 1, 2, 3, 6 and 12 months after initiation of phototherapy in comparison with those in blood taken immediately before phototherapy.

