10.6 Biomarker Studies

All participants will be asked to donate blood at each follow-up. The blood samples will be principally used for assay of measures of the function of blood immune cells, as well as markers in serum such as 25(OH)D. Gene expression patterns in the blood cells will also be studied. The kinetics of changes in any of these biomarkers due to phototherapy will be analysed. In the healthy controls, gene expression patterns (transcriptome analyses of cells in whole blood) and vitamin D levels in serum will be measured.

Permission will be sought from the patients diagnosed with CIS to use samples of blood to create a serum, whole blood, DNA, and RNA bank for subsequent scientific studies related to MS progression.

11. Advertising

There will be no advertisements for participants of this study, except for the healthy controls who will donate blood 11 ml blood monthly for 12 months, or a larger donation of blood on a single occasion. Posters have been prepared to recruit the healthy controls from the Telethon Kids Institute, Subiaco, Western Australia.

12. Research involving ionizing radiation

Not applicable as narrow band UVB radiation is not ionizing radiation.

13. Inclusion Criteria

For inclusion in this study, a participant must meet the following criteria:

- Aged between 18 and 65 years old inclusive.
- Recently diagnosed (<120 days) with a first isolated, well-defined, uni- or multi-focal first demyelinating event (FDE).
- Able to receive their first phototherapy within 120 days of FDE symptom onset.
- An MRI brain scan that is supportive of demyelinating disease (Paty A or Paty B criteria, i.e. the presence of at least four T2 lesions greater than 3 mm, or at least three T2 lesions greater than 3 mm, one of which must be periventricular, respectively).
- An EDSS between 0 6.5 (inclusive)
- Must be able to give informed consent and sign the informed consent form
- Must be able to comply with all study procedures, and attend 24 phototherapy sessions and centres for venepuncture on multiple occasions during and after phototherapy
- If female of child-bearing age, must be willing to use effective contraception
- Must be willing to avoid use of sunbeds
- Must be able to stand in the phototherapy cubicle for up to 5 minutes at a time

14. Exclusion Criteria

Any of the following conditions will exclude a participant from the study:

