Appendix 1: Study Schedule

Action	Initial		After conf	firmation of	participatio	n: Randomi	sed to UVB ph	ototherapy or	No photothera	
	Screen/ Baseline	0	1 wk	1 mth	2 mth	3 mth	6 mth	12 mth	Early withdrawal/ Exit	Unscheduled Visit
Informed consent	N									
Selection Criteria	N	N Only if								
Urine and serum Pregnancy Test	N^1	>1 month since								
Imaging by MRI	N	screening bloods (due to				\pm^{N}	N	N	N	+ N
Neurological Review (incl EDSS)	N	steroids)				N	N	N	N	N
Report adverse events			N	N	N	N	N	N	N	N
Medical Review	N					N	N	N	N	N
Discuss any symptom changes	-		ST	ST	ST	N	N	N	N	N
Concomitant medications	N		ST	ST	ST	N	N	N	N	N
Neurological Tests (incl KFS, MSFC)	ST			ST	ST	ST	ST	ST	ST	ST
Anthropometric measures, blood pressure	ST							ST	ST	
Weight, blood pressure				ST	ST	ST	ST			
Eye/skin/hair colour, Skin reflectance,	ST							ST	ST	

Silicon cast										
Questionnaires (Lifestyle, SF36QoL, FSS)	ST						ST	ST	ST	
Skin assessment by consultant dermatologist	N N						N			
Saliva collection for EBV analysis	X		X	X	X	X	X	X	X	
Blood taken for assessing Blood Transcriptome	ment of the	following:	X	X	X	X	X	X	X	
Serum 25(OH)D	X	Only if					X		X	
Immunophenotyping	X	>1 month since	X	X	X	X	X	X	X	
PBMC (FoxP3 assay)	X	screening bloods	X	X	X	X	X	X	X	
PBMC (DC assay)	X	(due to steroids)	X	X	X	X	X	X	X	

Narrow band UVB Phototherapy

N = As assessed by the investigator Neurologist

ST = As assessed by member of the \underline{S} tudy \underline{T} eam (dark shading)

X = Blood taken for assessment of biomarkers

¹ For child bearing potential females only

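### Section 10.3 and Appendix 1 set different triggers for the repeat pre-phototherapy biomarker blood, and the Appendix 1 trigger can miss patients screened less than a month after steroids

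*Protocol*

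**What the plan says.** Section 10.3 covers a defined group: "If participants randomised to receive narrow band UVB phototherapy have been given a short course of glucocorticoids to treat their symptoms". For them, "the participants will be asked to commence UVB phototherapy in one month after completion of glucocorticoids". The reason given is that "This will allow a drug-washout period and normalization of their immunological biomarkers". After that interval, "immediately prior to the start of phototherapy, they will be asked to donate 50 ml blood for pretherapy measurement of biomarkers". The only trigger is a steroid course in a participant allocated to UVB.

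Appendix 1 puts a condition on its visit 0 column. The cell is broken across rows in the extracted text, but its pieces appear twice, once beside the clinical rows and once beside the blood rows. They read as permitting the visit 0 items only if ">1 month since" the "screening bloods (due to" steroids). The reference point is therefore the screening blood. The heading above the column covers both randomised groups.

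Aim 3 in section 7 compares later samples "in comparison with those in blood taken immediately before phototherapy". Section 8.6 lists five primary endpoints, of which four are phototherapy-associated changes in blood biomarkers.

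**The concern.** The two places govern the same sample but start their clocks at different events, and neither says which prevails. Section 10.3 treats blood drawn less than a month after steroids as not yet normalised. If steroids ended shortly before the screening blood, the washout can finish less than a month after that blood. Appendix 1 then calls for no repeat, and the screening blood remains the baseline.

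This order of events is plausible. Steroids are given for the event that leads to screening, section 10.3 describes the course as a few days long, and the inclusion criteria in section 13 leave room for a washout: "Able to receive their first phototherapy within 120 days of FDE symptom onset".

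What is at stake is the reference value for the four biomarker primary endpoints. In a within-patient comparison, recovery from steroids after such a baseline cannot be told apart from an effect of phototherapy.

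**Working it through.** The documents give no figure to reproduce, so the check is a timeline.

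**Inputs**
- Washout: one month from steroid completion to first phototherapy, UVB arm (section 10.3).
- Appendix 1 trigger: more than one month from screening blood to visit 0.
- Assumptions: one month = 30 days, and phototherapy starts d days after the washout ends, with d = 0, 7, 14 or 30.

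**Formula.** Let steroids end s days before the screening blood. For s from 1 to 29:
- days from screening blood to phototherapy = 30 − s + d
- the Appendix 1 trigger is met if 30 − s + d > 30, that is, if s < d
- the screening blood lies inside the washout, because s < 30.

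| Delay d (days) | Gap from screening blood to start | Trigger met for | Trigger not met, screening blood inside washout |
|---|---|---|---|
| 0 | 30 − s | none | s = 1 to 29 |
| 7 | 37 − s | s = 1 to 6 | s = 7 to 29 |
| 14 | 44 − s | s = 1 to 13 | s = 14 to 29 |
| 30 | 60 − s | s = 1 to 29 | none |

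For example, with s = 10 and d = 0 the gap is 30 − 10 = 20 days. Section 10.3 requires the repeat and Appendix 1 does not allow it.

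**Outside that range**
- s = 0, d = 0: the gap is exactly 30 days, which does not exceed 30, so the trigger is not met.
- s of 30 or more: the washout was complete before the screening blood, so that sample is acceptable by the protocol's own standard.
- Steroids ended k days after the screening blood (k at least 1): the gap is at least 30 + k > 30, and the two rules agree.

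**Arms.** The section 10.3 repeat applies only to participants randomised to UVB, while the Appendix 1 column stands under both arms. Section 10.3 gives steroid-treated controls neither a washout nor a repeat sample, and section 10.4.2 dates their visits from randomisation.

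**Blood volume.** The synopsis gives 50 ml at seven time points and a maximum of 360 ml. Seven draws make 7 × 50 = 350 ml. The section 10.3 repeat makes 8 × 50 = 400 ml, which is 40 ml over the maximum.

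**The case against.** The best defence is that the body text already orders the right sample for the UVB arm. Section 10.3 has no interval condition, aim 3 names blood taken just before phototherapy as the comparator, and section 8.2 places baseline before phototherapy begins. Nothing in Appendix 1 claims to override this, and its reference to steroids suggests that the cell is shorthand for the section 10.3 washout. This stands in part: the affected baseline arises only where staff work from the table. But sections 10, 10.4 and 10.4.2 send staff to Appendix 1 for the schedule, and as worded it gives a different instruction.

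A second defence is randomisation. Section 19.4.2 tests differences between groups, and steroid recovery would be expected in both arms. This also stands in part. It does not protect the within-patient comparison of aim 3, and it is weakened if only the UVB arm gets a post-washout baseline.

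A reader might infer that the Appendix 1 trigger can never fire for anyone whose steroids ended before screening, or that all such patients have a steroid-affected baseline. The documents do not support either. A delayed start can meet the trigger, and patients a month or more past steroids at screening already have a washed-out sample.

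**Conclusion.** The inconsistency is real and should be corrected. With a 30-day month and an on-schedule start, patients whose steroids ended 1 to 29 days before the screening blood get a repeat sample under section 10.3 but not under Appendix 1. The range narrows to 7 to 29 days with a 7-day delay and 14 to 29 with a 14-day delay, and closes with a 30-day delay. The documents do not say how many participants fall in it.

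If Appendix 1 is followed, those patients keep a baseline that the protocol itself regards as not normalised, and the aim 3 changes mix steroid recovery with phototherapy. It would go too far to conclude that the randomised comparison is biased. That is not shown. What can be said is that baseline timing may differ by arm, because the two places differ on whether controls are covered.

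**What to change.** Reconcile section 10.3 and Appendix 1 so that one sampling rule applies:

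- Key the Appendix 1 visit 0 condition to the same steroid-based trigger as section 10.3, in place of time since the screening bloods.
- State whether the rule covers steroid-treated controls, so that baseline is defined in the same way in both arms.
- Define the analysis baseline as the last sample before day 0, and say what day 0 is for a control. Record steroid timing and use it as a covariate or in a sensitivity analysis. Accepting only samples drawn at least a month after steroids would be a poor substitute, since a control with no washout could then be left without a baseline.
- Check the 360 ml maximum against the 400 ml that seven draws plus a repeat require.

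The cost is one table cell, one baseline definition and possibly one extra draw in some steroid-treated participants. No change to steroid treatment or to the timing of phototherapy is proposed.

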10.3.1 Sun exposure

Participants will be asked to avoid tanning salons and sun beds. Reference material on the current sun exposure guidelines, as advised by the Cancer Council Australia, will be provided on request (www.cancerwa.asn.au/prevention/sunsmart). Participants should not stay in the sun for sufficient time to cause reddening of the skin. This trial is being performed in winter to avoid sun exposure.

A silicone skin cast of the back of the hand will be prepared from all participants. This will allow us to test whether past sun exposure modifies the immune response to phototherapy. This provides a reliable and validated estimate of actinic damage secondary to cumulative sun exposure [17,44].

10.4 Follow-Up Visits

There will be seven study time-points (Appendix 1, Study Schedule), namely (1) before phototherapy (see above), (2) after the first week of phototherapy, (3) after 1 month of

phototherapy (mid-intervention), (4) after 2 months of phototherapy (end of intervention), (5) after 3 months, (one month after termination of phototherapy), (6) 6 months, (four months after phototherapy, and (7) 12 months, (10 months after phototherapy).

10.4.1 The 1 week visit

Members of the Study Team will confirm that no adverse event has taken place due to narrow band UVB exposure. Blood will be collected for measurement of biomarkers and isolation of peripheral blood mononuclear cells for functional assays. Any change in symptoms or medications will be recorded.

10.4.2 Study visits at 1 month, 2 months, 3 months, and 6 months since start of phototherapy (or randomisation into the non-phototherapy group)

Participants will be reviewed as per the study schedule (Appendix 1).

Participants will have an appointment with their neurologist after 3 and 6 months. After 1 and 2 months, participants will meet one of the study team unless any symptoms require neurologist review.

- Blood collection for measurement of biomarkers and isolation of peripheral blood mononuclear cells for functional assays (1, 2, 3 and 6 months)
- Gadolinium-enhanced cerebral MRI (after 3 months if neurologist feels necessary, after 6 months for all participants)
- Clinical evaluations with review of any adverse events, intercurrent medical events and updated concomitant medications (1, 2, 3 and 6 months)
- Serial Questionnaires (6 months, see Appendices).
- KFS, MSFC (1, 2, 3 and 6 months).
- Measures of weight, blood pressure (1, 2, 3 and 6 months). Participants will be asked to remove clothing to allow placement of a blood pressure cuff on their arm
- Saliva collection for EBV measurement

10.4.3 Final Visit 12 months since start of phototherapy (or randomisation into the non-phototherapy group)

Participants will be reviewed by both a neurologist and a member of the study team as per study schedule (Appendix 1, Study schedule).

- Blood collection for measurement of biomarkers and isolation of peripheral blood mononuclear cells for functional assays
- Gadolinium-enhanced cerebral MRI
- Clinical evaluations with review of relapse history, adverse events, intercurrent medical events and updated concomitant medications
- EDSS, KFS, MSFC.
- Fatigue Severity Scale, SF-36, Exit questionnaires (See Appendices).

- Anthropometric measurements (weight, height, waist and hip circumference), blood pressure. Participants will be asked to remove clothing to allow waist and hip measurement and placement of a blood pressure cuff on their arm
- Eye/skin/hair colour assessment
- Assessment of skin reflectance and preparation of a silicone cast of the back of the hand
- Saliva collection for EBV measurement

10.4.4 Unscheduled Visits (Relapse or Adverse Event Visit)

Participants will be encouraged to report any new symptoms to the study team within 48 hours of occurrence. If significant new or worsening neurological symptoms suspicious for a relapse are present, or if a potential adverse event has occurred, then an unscheduled visit should be arranged as soon as possible (ideally within 4 days of symptom onset).

The following assessments should be undertaken at the unscheduled visit:

• History of new symptoms

If suspicious of a relapse:

- KFS/EDSS
- Relapse treatment as indicated

If suspicious of an adverse event:

- Initiation of appropriate investigations and management.
- Documentation of potential adverse event to be sent to the Co-ordinating Principal Investigator for review by the Data Safety Monitoring Board (if Serious AE).
- If a serious adverse event was managed by another doctor/hospital, then the Coordinating Principal Investigator should make all reasonable attempts to obtain relevant documentation.

10.4.5 Early Termination Visit

If a participant exits the study for any reason (including inability to complete 24 phototherapy sessions in 12 weeks), an early termination visit will be organised as soon as possible.

This visit will comprise

- Blood collection for measurement of biomarkers and isolation of peripheral blood mononuclear cells for functional assays
- Gadolinium-enhanced cerebral MRI (exit scan)
- Clinical evaluations with review of relapse history, adverse events, intercurrent medical events and updated concomitant medications
- EDSS, KFS, MSFC
- Fatigue Severity Scale, SF-36, Exit questionnaires
- Anthropometric measurements (weight, height, waist and hip circumference), blood pressure

Eye/skin/hair colour assessment

Assessment of skin reflectance and preparation of a silicone cast of the back of the hand.

